6.7. Intervention after the End of the Study

Not applicable.

7. Discontinuation of Study Intervention and Participant Discontinuation/Withdrawal

These sections describe reasons for a participant's

- permanent or temporary discontinuation of study intervention, or
- discontinuation (withdrawal) from the study.

Discontinuation of the trial as a whole is handled as part of regulatory, ethical, and trial oversight considerations in Appendix 1 (Section 10.1).

7.1. Discontinuation of Study Intervention

Not applicable.

7.2. Participant Discontinuation/Withdrawal from the Study

A participant may withdraw from the study

- at any time at his/her own request
- at the request of his/her designee (for example, parents or legal guardian)
- at the discretion of the investigator for safety, behavioral, compliance, or administrative reasons
- if the participant becomes pregnant during the study
- if enrollment in any other clinical study involving an investigational product or enrollment in any other type of medical research judged not to be scientifically or medically compatible with this study

At the time of discontinuing from the study, if possible, an early discontinuation visit should be conducted, as shown in the SoA. See SoA for data to be collected at the time of study discontinuation and follow-up and for any further evaluations that need to be completed. The participant will be permanently discontinued both from the study intervention and from the study at that time.

If the participant withdraws consent for disclosure of future information, the sponsor may retain and continue to use any data collected before such a withdrawal of consent. If a participant withdraws from the study, he/she may request destruction of any samples taken and not tested, and the investigator must document this in the site study records.

7.2.1. Discontinuation of Inadvertently Enrolled Participants

If the sponsor or investigator identifies a participant who did not meet enrollment criteria and was inadvertently enrolled, then the participant should be discontinued from study treatment and safety follow-up should be performed as outlined in

- Section 1.3 (SoA),
- Section 8.2 (Safety Assessments), and
- Section 8.3 (Adverse Events and Serious Adverse Events).

7.3. Lost to Follow up

A participant will be considered lost to follow-up if he or she repeatedly fails to return for scheduled visits and is unable to be contacted by the study site. Site personnel are expected to make diligent attempts to contact participants who fail to return for a scheduled visit or were otherwise unable to be followed up by the site.

8. Study Assessments and Procedures

Study procedures and their timing are summarized in the SoA (Section 1.3).

Immediate safety concerns should be discussed with the sponsor immediately upon occurrence or awareness to determine if the participant should continue or discontinue study intervention.

Adherence to the study design requirements, including those specified in the SoA, is essential and required for study conduct.

All screening evaluations must be completed and reviewed to confirm that potential participants meet all eligibility criteria. The investigator or designee will maintain a screening log to record details of all participants screened and to confirm eligibility or record reasons for screening failure, as applicable.

8.1. Efficacy Assessments

Not applicable.

8.2. Safety Assessments

Planned time points for all safety assessments are provided in the SoA.

8.2.1. Physical Examinations

A complete physical examination will include, at a minimum, assessments of the cardiovascular, respiratory, gastrointestinal, dermatological, and neurological systems. Height and weight will also be measured and recorded at screening.

Investigators should pay special attention to clinical signs related to COVID-19.

8.2.2. Vital Signs

For each participant, vital sign measurements should be conducted according to the SoA (Section 1.3). Additional vital signs may be measured during each study period at the investigator's judgment. Blood pressure and pulse rate should be measured after at least 5 minutes supine.

Orthostatic vital signs should be assessed, if possible, during any AE of dizziness or posture-induced symptoms. If orthostatic measurements are required, participants should be supine for at least 5 minutes and stand for at least 3 minutes. If the participant feels unable to stand, supine vital signs only will be recorded.

Additional vital signs may be measured during each study period, if warranted.

8.2.3. Electrocardiograms

A single, local, 12-lead ECG will be obtained as shown in the SoA, using an ECG machine that automatically calculates the heart rate and measures pulse rate, QRS, QT, and corrected QT intervals. Additional ECG readings may occur at investigator discretion.

8.2.4. Clinical Safety Laboratory Assessments

See Appendix 2 (Section 10.2) for the list of clinical laboratory tests to be performed and to the SoA for the timing and frequency.

All protocol-required laboratory assessments, as defined in Appendix 2, must be conducted in accordance with the laboratory manual and the SoA.

The investigator must review the laboratory report, document this review, and record any clinically relevant changes occurring during the study in the AE section of the CRF. The laboratory reports must be filed with the source documents.

If laboratory values from nonprotocol-specified laboratory assessments performed at the institution's local laboratory require a change in participant management or are considered clinically significant by the investigator (for example, SAE or AE or dose modification), then the results must be recorded in the CRF.

8.2.5. Injection Site Reaction Assessment

Injection site assessments using the ISR CRF, VAS if required (see below), and an exploratory tool (Scarletred) will be performed at times specified in the SoA (Section 1.3).

Injection site pain assessments are part of the solicited and spontaneous ISR assessments. The baseline assessment, and all positive responses of pain from then on, will require an additional assessment using the Pain VAS.

As there are multiple injections for each dose, ISR assessments will be done for each injection. Manifestations of a local ISR may include erythema, induration, pain, pruritus, and edema. Injection site findings will be captured on the eCRF.

Injection site reactions, if recorded as a result of the prespecified (or solicited) assessment, will be recorded as AEs only if they qualify as SAEs.

If a spontaneous (or unsolicited) ISR is reported by a participant or investigator, the ISR CRF will be used to capture additional information about this reaction (for example, degree and area of erythema) at additional visits until resolution of the event.

The VAS is a well-validated tool (Williamson and Hoggart 2005) to assess injection site pain; it is presented as a 100-mm line anchored by verbal descriptors, usually "no pain" and "worst imaginable pain." The participant will be asked to rate any pain at the injection site on a scale of 0 to 100 on the line, as soon as possible following each injection.

In addition, the exploratory tool (Scarletred) will be used to acquire exploratory ISR data at each of the time points where the ISR data is being collected by administration of the ISR CRF. Failure to take this assessment at any of the indicated time points will not result in a protocol deviation.

8.3. Adverse Events and Serious Adverse Events

Adverse events will be reported by the participant.

The investigator and any qualified designees are responsible for detecting, documenting, and recording events that meet the definition of an AE or SAE and remain responsible for following up AEs that are serious, considered related to the study intervention or study procedures, or that caused the participant to discontinue the study intervention or study.

Discontinuation information is in Section 7.

Detailed AE definitions and procedures are in Section 10.3.

8.3.1. Time Period and Frequency for Collecting AE and SAE Information

All AEs and SAEs will be collected from the time of signing of the ICF until participation in the study has ended.

Adverse events that begin before the start of study intervention, but after signing of the ICF will be recorded on the AE CRF.

Although all AEs after signing the ICF are recorded by the site in the CRF/electronic data entry, SAE reporting to sponsor begins after the participant has signed the ICF and has received study intervention. However, if an SAE occurs after signing the ICF, but prior to receiving study intervention, it needs to be reported within the SAE reporting time frame if it is considered reasonably possibly related to study procedures.

All SAEs will be recorded and reported to the sponsor or designee immediately and under no circumstance should this exceed 24 hours, as indicated in Section 10.3, Appendix 3. The investigator will submit any updated SAE data to the sponsor within 24 hours of it being available.

Investigators are not obligated to actively seek AEs or SAEs after conclusion of the study participation (Day 85). However, if the investigator learns of any SAE, including a death, at any time after a participant has been discharged from the study, and he/she considers the event to be reasonably related to the study intervention or study participation, the investigator must promptly notify the sponsor.

8.3.2. Method of Detecting AEs and SAEs

The method of recording, evaluating, and assessing causality of AE and SAE and the procedures for completing and transmitting SAE reports are provided in Section 10.3, Appendix 3

Care will be taken not to introduce bias while detecting AEs and/or SAEs. Open-ended and nonleading verbal questioning of the participant is the preferred method to inquire about AE occurrences.

8.3.3. Follow-up of AEs and SAEs

After the initial AE/SAE report, the investigator is required to proactively follow each participant at subsequent visits/contacts. All SAEs will be followed up until resolution, stabilization, the event is otherwise explained, or the participant is lost to follow-up (as defined in Section 7.3). Further information on follow-up procedures is provided in Section 10.3, Appendix 3.

8.3.4. Regulatory Reporting Requirements for SAEs

Prompt notification by the investigator to the sponsor of an SAE is essential so that legal obligations and ethical responsibilities toward the safety of participants and the safety of a study intervention under clinical investigation are met.

The sponsor has a legal responsibility to notify both the local regulatory authority and other regulatory agencies about the safety of a study intervention under clinical investigation. The sponsor will comply with country-specific regulatory requirements relating to safety reporting to the regulatory authority, IRB/IEC, and investigators.

An investigator who receives an investigator safety report describing an SAE or other specific safety information (for example, summary or listing of SAEs) from the sponsor will review and then file it with the IB, and will notify the IRB/IEC, if appropriate according to local requirements.

8.3.5. Pregnancy

Details of all pregnancies in female participants and female partners of male participants will be collected after the start of study intervention and until at least 5 months after the last dose.

If a pregnancy is reported, the investigator should inform the sponsor within 24 hours of learning of the pregnancy and should follow the procedures outlined in Section 10.4, Appendix 4

Abnormal pregnancy outcomes (for example, spontaneous abortion, fetal death, stillbirth, congenital anomalies, ectopic pregnancy) are considered SAEs.

8.3.6. Hypersensitivity Reactions

Many drugs, but particularly biologic agents, carry the risk of systemic hypersensitivity reactions. If such a reaction occurs, additional details describing each symptom should be provided to the sponsor in the Hypersensitivity/Anaphylactic/Infusion-Related Reaction CRF.

Sites should have appropriately trained medical personnel and appropriate medical equipment available when study participants are receiving intervention. It is recommended that participants who experience a systemic hypersensitivity reaction be treated per national and international guidance (Lieberman et al. 2015; Simons et al. 2015).

In the case of generalized urticaria or anaphylaxis, additional blood and urine samples should be collected as described in Section 10.6, Appendix 6, “Recommended Laboratory Testing for Hypersensitivity Events”. Laboratory results are provided to the sponsor via the central laboratory.

8.3.7. SARS-CoV-2 Infection

Site procedures for participant management will be followed in the event of a suspected SARS-CoV-2 infection during the study.

A nasopharyngeal swab will be taken on Day 1 and shipped to the sponsor. This is for research purposes, such as viral sequencing.

In addition, SARS-CoV-2 point-of-care tests may be performed at specific timepoints during the study at the discretion of the investigator. Every time such a point-of-care test is performed post

baseline, an additional nasal swab sample may be collected in parallel, for research purposes such as viral sequencing. This research swab sample will be shipped to the sponsor only if the point-of-care test is positive. If the point-of-care test is negative, the research swab sample should be discarded.

8.3.8. Product Complaints

A product complaint is any written, electronic, or oral communication that alleges deficiencies related to the identity, quality, durability, reliability, safety, effectiveness, or performance of a trial intervention.

The sponsor collects product complaints on study interventions used in clinical studies to ensure the safety of study participants, monitor quality, and to facilitate process and product improvements.

Participants will be instructed to contact the investigator as soon as possible if they have a complaint or problem with the study intervention so that the situation can be assessed.

NOTE: Any AEs or SAEs that are associated with a product complaint will follow the processes outlined in Section 8.3.3 and Section 10.3, Appendix 3, of the protocol.

Time Period for Detecting Product Complaints

Product complaints that result in an AE will be detected, documented, and reported to the sponsor during all periods of the study in which the study intervention is used.

If the investigator learns of any product complaint at any time after a participant has been discharged from the study, and such incident is considered reasonably related to the study intervention, the investigator will promptly notify the sponsor.

Prompt Reporting of Product Complaints to Sponsor

Product complaints will be reported to the sponsor within 24 hours after the investigator becomes aware of the complaint.

The Product Complaint Form will be sent to the sponsor by a method designated by the sponsor.

Follow-up of Product Complaints

Follow-up applies to all participants, including those who discontinue study intervention.

The investigator is responsible for ensuring that follow-up includes any supplemental investigations as indicated to elucidate the nature and/or causality of the product complaint.

New or updated information will be recorded on the originally completed form with all changes signed and dated by the investigator and submitted to the sponsor.

8.4. Treatment of Overdose

For the purposes of this study, an overdose of LY3819253 is considered any dose higher than the dose assigned through randomization. In case of suspected overdose, participants should be monitored for any signs or symptoms of adverse reactions or effects, and supportive care should be provided as necessary.

8.5. Pharmacokinetics

Venous blood samples will be collected as specified in the SoA for determination of serum concentrations of LY3819253 used to evaluate the PK for LY3819253.

A maximum of 5 samples may be collected at additional time points during the study, if warranted and agreed upon between the investigator and the sponsor.

Instructions for the collection and handling of biological samples will be provided by Lilly.

Site personnel will record

- the date and time (24-hour clock time) of investigational drug administration, and
- the date and time (24-hour clock time) of each PK sample.

It is essential that the times are recorded accurately.

8.5.1. Bioanalytical

Samples will be analyzed at a laboratory approved by the sponsor and stored at a facility designated by the sponsor. Concentrations of LY3819253 will be assayed using a validated bioanalytical method. Analyses of samples collected from placebo-treated subjects are not planned.

Sample retention is described in Appendix 1, Section 10.1.10. Remaining samples used for PK may be pooled and used for exploratory metabolism or bioanalytical method experiments as deemed appropriate.

8.6. Pharmacodynamics

Pharmacodynamic parameters will not be evaluated in this study.

8.7. Genetics

A whole blood sample will be collected for pharmacogenetic analysis where local regulations allow.

See Section 10.2, Clinical Laboratory Tests, and Section 1.3 SoA for sample collection information.

See Section 10.5 for genetic research, custody, and sample retention information.

8.8. Biomarkers

Serum samples for exploratory biomarker research will be collected at the time specified in the SoA where local regulations allow.

Samples will be stored and analysis may be performed on biomarkers thought to play a role in immune system-related responses to viral infection or administration of LY3819253 including, but not limited to, immune pathways or serum analytes to evaluate their association with LY3819253 administration.

Samples may be used for research to develop methods, assays, prognostics, and/or companion diagnostics related to the intervention target (spike protein), pathways associated with disease, and/or the mechanism of action of the study intervention.

Swab samples taken during the study may be used for research purposes, such as viral sequencing.

Sample retention is described in Section [10.1.10](#).

8.9. Immunogenicity Assessments

Visits and times

At the visits and times specified in the SoA, predose venous blood samples will be collected to determine antibody production against LY3819253. The actual date and time (24-hour clock time) of each sample collection will be recorded. To aid interpretation of these results, the immunogenicity sampling timepoints all coincide with a PK sampling timepoint.

Sample collection, handling, and use

Instructions for the collection and handling of blood samples will be provided by the sponsor.

Immunogenicity will be assessed using a validated assay designed to detect ADAs in the presence of LY3819253 at a laboratory approved by the sponsor. Antibodies may be further characterized for their ability to neutralize the activity of LY3819253.

Sample retention

Sample retention is described in Section [10.1.10](#).

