AE review	X	X	Predose	X	X	X	X	X	X	X	X	X	X	AEs to be reviewed only after participant has signed the study ICF.
HIV, hepatitis B/C serology	X													

Procedure / Assessments	Screening	Treatment Period								Follow-up Visits				Comment
Visit Number	V1	V2								V3	V4	V5	V6/ED	
Week(s)		0								2	4	8	12	
Study Day	-14 to -1	-1	1	2	3	4	5	6	7	15 ±2d	29 ±3d	60 ±3d	85 ±3d	
Pregnancy test (women only) ^b	X	X											X	Serum pregnancy test at screening, urine test at other timepoints. Day -1 urine test refers to test at admission; this is not needed if admissions is on the same day as screening. Postdose urine test(s) can be performed at the judgment of the investigator, if pregnancy is suspected.
Clinical laboratory tests ^a	X	X							X	X	X	X	X	Fasting is not required for these tests. If screening takes place on Day -1, there is no need to conduct these tests twice on Day -1.
Breath or urine ethanol screen		X												Ethanol screen may be repeated at other time points at the discretion of the investigator.
Urine drug screen	X	X												Day -1 urine test refers to test at admission; this is not needed if admission occurs on the same day as screening. Drug screen may be repeated at other time points at the discretion of the investigator.

Procedure / Assessments	Screening	Treatment Period								Follow-up Visits				Comment
	Visit Number	V1	V2								V3	V4	V5	
Week(s)		0								2	4	8	12	
Study Day	-14 to -1	-1	1	2	3	4	5	6	7	15 ±2d	29 ±3d	60 ±3d	85 ±3d	
SC LY3819253 or placebo dosing			X											
LY3819253 PK sampling ^a			X	X	X	X	X	X	X	X	X	X	X	Day 1 collection should be taken up to 4h postdose ±4h. The exact time of draw must be recorded. For Day 2 onwards, PK samples may be taken at any time after vital signs.
Injection site assessments			Predose; 1min ±1min, 10min ±2min, 30min ±5min, 240min ± 10min	24h ±4h	X	X	X	X	X	X	X	X	X	Timepoints include ISR assessment, VAS, if pain is reported, and the exploratory Scarletred tool. Scarletred timing is flexible and not confined to the windows shown, except for predose. See Section 8.2.5 for detail.
Immunogenicity			Predose							X	X	X	X	
Serum sample for exploratory biomarkers ^a			Predose		X					X	X	X	X	
Pharmacogenetics sample ^a			Predose											For storage only.

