5.2. Exclusion Criteria

Participants are excluded from the study if any of the following criteria apply:

Medical Conditions

10. have current SARS-CoV-2 infection confirmed by nasal or nasal pharyngeal swab results at screening or Day -1.

11. have had prior SARS-CoV-2 infection within 6 weeks before screening, confirmed by either previous nucleic acid-based test, or previous serology
12. have suspected current SARS-CoV-2 infection, in the opinion of the investigator, based on either or both of the following:
 - a. a recent exposure to SARS-CoV-2, defined as:
 - living in the same household as a person with SARS-CoV-2;
 - having had direct physical contact with a person with SARS-CoV-2 (for example, shaking hands);
 - having unprotected direct contact with infectious secretions of a person with SARS-CoV-2 (for example, being coughed on or touching used paper tissues with a bare hand);
 - having had face-to-face contact with a person with SARS-CoV-2, within 2 meters and for more than 15 minutes
 - b. signs or symptoms that, in the opinion of the investigator, are suggestive of infection (for example, fever, dry cough, shortness of breath, hypoxia, etc.)
13. have a history or presence of cardiovascular (including hypertension), respiratory, hepatic, renal, gastrointestinal, endocrine, hematological, psychiatric, or neurological disorders that, in the opinion of the investigator, are capable of
 - a. significantly altering the absorption, metabolism, or elimination of drugs
 - b. constituting a risk while taking the investigational product, or
 - c. interfering with the interpretation of data
14. have clinically significant abnormal ECG results constituting a risk while taking the investigational product, as determined by the investigator
15. have an abnormal blood pressure as determined by the investigator. In case blood pressure appears to be abnormally high during the screening period, it is possible to repeat the measure(s) 1 time in a quiet room to avoid an exclusion due to the white coat effect
16. have significant allergies to humanized mAbs
17. have any of the following that are clinically significant:
 - a. multiple or severe drug allergies
 - b. intolerance to topical corticosteroids, or
 - c. severe posttreatment hypersensitivity reactions (including, but not limited to, erythema multiforme major, linear immunoglobulin A dermatosis, toxic epidermal necrolysis, or exfoliative dermatitis)

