10.2.1. Blood Sampling Summary

This table summarizes the approximate number of venipunctures and blood volumes for all blood sampling (screening, safety laboratories, and bioanalytical assays) during the study.

Purpose	Blood Volume per Sample (mL)	Number of Blood Samples	Total Volume (mL)
Screening tests ^a	45	1	45
Clinical laboratory tests ^a	15		
SARS-CoV-2 serology	10	5	50
Pharmacokinetics	4	12	48
Immunogenicity	10	5	50
Blood discard for cannula patency	1	5	5
Pharmacogenetics	10	1	10
Serum for exploratory biomarkers	10	6	60
Total			268
Total for clinical purposes (rounded up to nearest 10 mL)			270

^a Additional samples may be drawn if needed for safety purposes.

10.3. Appendix 3: Adverse Events: Definitions and Procedures for Recording, Evaluating, Follow-up, and Reporting

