- For PK profiles during multiple dosing, the concentration of the pre-dose sample exceeds all measured concentrations for that individual in the subsequent post-dose samples.
- For PK profiles during single dosing of non-endogenous compounds, the concentration in a pre-dose sample is quantifiable.
- For any questionable datum that does not satisfy the above criteria, the profile will be evaluated and results reported with and without the suspected datum.

Data between Individual Profiles

1. If $n < 6$, then the dataset is too small to conduct a reliable range test. Data will be analyzed with and without the atypical value, and both sets of results will be reported.

2. If $n \geq 6$, then an objective outlier test will be used to compare the atypical value to other values included in that calculation:
 - a. Transform all values in the calculation to the logarithmic domain.
 - b. Find the most extreme value from the arithmetic mean of the log transformed values and exclude that value from the dataset.
 - c. Calculate the lower and upper bounds of the range defined by the arithmetic mean $\pm 3 \times SD$ of the remaining log-transformed values.
 - d. If the extreme value is within the range of arithmetic mean $\pm 3 \times SD$, then it is not an outlier and will be retained in the dataset.
 - e. If the extreme value is outside the range of arithmetic mean $\pm 3 \times SD$, then it is an outlier and will be excluded from analysis.

If the remaining dataset contains another atypical datum suspected to be an outlier and $n \geq 6$ following the exclusion, then repeat step 2 above. This evaluation may be repeated as many times as necessary, excluding only one suspected outlier in each iteration, until all data remaining in the dataset fall within the range of arithmetic mean $\pm 3 \times SD$ of the log-transformed values.

Reporting of Excluded Values

Individual values excluded as outliers will be documented in the final report. Approval of the final report will connote approval of the exclusion.

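### The schedule has no pre-dose PK sample, contrary to Protocol 8.9 and one short of the blood table, so no planned analysis can check the primary AUC(0-∞) for background assay signal

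*Protocol*

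**What the plan says.** - **SoA (Protocol 1.3).** The PK row has one entry on each of Days 1 to 7 and one at each of Visits 3 to 6. For Day 1 the comment is "Day 1 collection should be taken up to 4h postdose ±4h"; for later days, "For Day 2 onwards, PK samples may be taken at any time after vital signs". The immunogenicity, exploratory biomarker and pharmacogenetic rows in the same schedule name a pre-dose time on Day 1. The PK row does not.
- **Protocol 8.9.** To help interpret the ADA results, "the immunogenicity sampling timepoints all coincide with a PK sampling timepoint".
- **Blood table (Protocol 10.2.1).** The PK row reads "Pharmacokinetics 4 12 48": 4 mL, 12 samples, 48 mL. The introduction to the table calls the counts approximate.
- **Protocol 8.5.1.** "Analyses of samples collected from placebo-treated subjects are not planned". The method is described only as validated.
- **SAP 9.3.1.** Pre-dose sampling times are set to zero. The pre-dose mean is set to zero for single-dose data on a non-endogenous compound. For single dosing, a value may be excluded if "the concentration in a pre-dose sample is quantifiable".
- **Protocol 5.2.** People are excluded if they "have had prior SARS-CoV-2 infection within 6 weeks before screening"; older infections are not excluded by that criterion. Serology is drawn on Day -1, but the result is not required before dosing.

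**The concern.** A pre-dose concentration is the usual blank for a single-dose PK profile. Without it, and with no planned assay of placebo serum, nothing planned would show whether the assay reads something other than drug.

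The question is not idle for this molecule. LY3819253 is a human IgG1 against the spike protein, with binding regions derived from a convalescent patient (Protocol 2.2 and 2.3). The entry criteria admit people infected more than 6 weeks before screening, who may carry natural antibody to the same target. If the assay read such antibody as drug, the signal would add to every concentration, raise AUC(0-∞) and flatten the terminal slope. The proportional effect would be larger at 350 mg than at 700 mg, so the geometric mean ratio between doses in SAP 9.3.2 could shift as well.

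Apart from that, three parts of the documents appear to expect a pre-dose sample that the SoA does not contain.

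**Working it through.** **1. Sample counts, SoA against 10.2.1**

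| Row | SoA | Blood table |
|---|---|---|
| PK | Days 1-7 (7) + Visits 3-6 (4) = 11 | 12 |
| Immunogenicity | pre-dose + Visits 3-6 = 5 | 5 |
| SARS-CoV-2 serology | Day -1 + Visits 3-6 = 5 | 5 |
| Exploratory biomarkers | pre-dose + Day 3 + Visits 3-6 = 6 | 6 |
| Pharmacogenetics | pre-dose = 1 | 1 |

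Of these rows only PK disagrees. The plan's total is 45 + 50 + 48 + 50 + 5 + 10 + 60 = 268 mL. With 11 PK samples (44 mL) it would be 264 mL.

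**2. ADA and PK pairing.** Visits 3, 4, 5 and 6 have both samples. Day 1 pre-dose has ADA only. That is 4 of 5, against all in 8.9.

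**3. The Day 1 window.** Read as 4 h ± 4 h, it runs from 0 to 8 h after dosing. It could also be read as 0-4 h ± 4 h, reaching back to 4 h before dosing. Either way it is a single draw labelled post-dose, so the count stays at 11.

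**4. With one pre-dose PK sample added.** PK 11 + 1 = 12; 12 × 4 = 48 mL; total 268 mL; pairing 5 of 5; the SAP check has a value to act on.

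**5. Possible size of undetected background**

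From the documents: AUC(0-∞) of 54000 hr*µg/mL at 700 mg IV (Protocol 4.3), so clearance is 700/54000 × 24 = 0.311 L/day, against about 0.3 in 2.2.1.2; half-life 14 to 28 days; SoA nominal times; the SAP rule of linear trapezoids up to tmax and logarithmic after.

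Assumed: one-compartment SC model, bioavailability F 0.5 to 0.8, absorption rate 0.3/day, terminal fit on the last three samples, and a constant background b at every post-dose sample in an affected participant. The documents give no assay format, quantification limit or background, so b is shown over a range.

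| b (µg/mL) | Rise in AUC(0-∞), 350 mg | 700 mg |
|---|---|---|
| 0.01 | 0.1-0.3% | about 0.1% |
| 0.1 | 1.3-2.6% | 0.7-1.3% |
| 0.5 | 7-14% | 3-7% |
| 1 | 14-28% | 7-14% |

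Hand check of the largest value: true AUC is 0.5 × 350 × 54000/700 = 13500 hr*µg/mL. A background of 1 µg/mL over 84 days adds about 84 × 24 = 2016, or 15%. The rest comes from extrapolating a flatter terminal slope. At 350 mg and b = 1, a true half-life of 21 days is estimated as 25 to 28 days.

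**6. Effect on a cohort.** If 1 of 7 participants is affected, the geometric mean is multiplied by (1 + rise)^(1/7). At b = 1, 1.28^(1/7) = 1.036, a rise of 3.6%. At b = 0.5, 1.14^(1/7) = 1.019, a rise of 1.9%.

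**The case against.** Four stronger readings are tempting, and the documents do not support them.

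- *Background could never be detected.* Placebo samples are collected and their assay is only not planned. PK samples are kept for up to 2 years. Pre-dose blood for ADA and pre-dose biomarker serum are kept for up to 15 years (10.1.10). Up to 5 extra PK samples may be agreed (8.5). A blank could be run ad hoc; what is missing is a planned one.
- *The primary result is biased.* Nothing shows that the assay reads natural anti-spike antibody. The laboratory reports in ng/mL, so the two larger cases above are backgrounds of 500 and 1000 ng/mL held for 85 days, a scale for which the documents offer no support. Without background the bias is nil. The cohort shift is also small beside the precision target in Protocol 9.2, a 90% confidence interval within (0.7, 1.43).
- *The SAP is contradicted.* Its outlier text is generic and optional, and the same list carries a multiple-dosing rule that cannot apply in this study. The pre-dose rule is left inoperative, which is weaker than a conflict.
- *The twelfth sample in the blood table is a pre-dose sample.* The table does not label it, and its counts are approximate. A pre-dose sample is simply the reading that reconciles the table, 8.9 and the SAP together.

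It is also fair to say that serology on Day -1 and at each follow-up visit would identify participants with natural antibody, and that the lost pairing at pre-dose matters little for reading ADA because no drug is expected then. Serology cannot, however, show whether the PK assay responds to that antibody.

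What remains is the conflict between the SoA and 8.9, the count of 11 against 12, and the lack of any planned blank for the primary endpoint.

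**Conclusion.** The point holds as an internal inconsistency with a modest bearing on the primary endpoint. The contradiction with 8.9 and the mismatch with 10.2.1 follow from the text by counting and need no assumption. That no planned analysis can detect background in AUC(0-∞) follows from the SoA together with 8.5.1.

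The size of any bias is conditional. It ranges from nil, through 0.1-0.3% at 0.01 µg/mL, to 14-28% at 1 µg/mL in an affected 350 mg participant, and it rests on the assumed bioavailability, absorption rate and constant background. For one affected participant of 7, the cohort geometric mean moves by at most about 4% over that range. This is a cheap improvement, and it gives no ground for saying that AUC(0-∞) will be wrong.

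**What to change.** In SoA 1.3, add *Predose* to the Day 1 PK cell and keep the post-dose draw. Take the tube at the pre-dose venipuncture already scheduled for ADA, biomarker and pharmacogenetic samples. The SoA, 8.9 and 10.2.1 then agree on 12 samples. State the Day 1 post-dose window without ambiguity at the same time.

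Keep the pre-dose check in SAP 9.3.1 and add one sentence: if a pre-dose value is quantifiable, AUC(0-∞) is reported with and without that participant, alongside the Day -1 serology result.

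Cost: one 4 mL tube already counted in the stated 48 mL, no added venipuncture, and one extra assay per LY3819253 participant.
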